**Background and Significance**

Pelvic fractures represent a small percent of all skeletal injuries but are associated with significant morbidity and mortality. They commonly result from high-energy trauma, particularly blunt trauma, as a significant force (an average of more than 3,000 N) must be imparted to disrupt the pelvic ring (Grimm 1989). Pelvic fractures are frequently associated with significant head, thoracic, abdominal, and extremity injuries as well as hemodynamic instability due to bleeding from cancellous bone surfaces and disrupted pelvic vasculature. Patients hypotensive at the scene and upon arrival at the definitive treatment facility have increased mortality relative to normotensive patients (Gabbe 2011, Sathy 2009). Stabilization of the pelvic ring reduces pelvic volume, decreases bleeding from bony surfaces, and stabilizes early hematoma (Grimm 1989).

Multiple techniques of pelvic reduction and stabilization have been described in the literature. These include spica casts, pneumatic antishock garments (e.g. MAST), anterior or posterior C-clamps, circumferential pelvic antishock sheeting (CPAS), commercially available external compression devices (i.e. pelvic binders), external fixation, closed reduction and percutaneous fixation, and open reduction and internal fixation. Today, CPAS and external compression with commercial pelvic binders are the most common prehospital techniques for supporting patients with hemodynamic instability and suspected pelvic fractures. Temporary pelvic splinting with these devices is now recommended in the initial management of hemodynamically unstable patients (Cuillinane 2011; White 2009; American College of Surgeons 2008). Not only are they relatively easy to apply in the prehospital setting and Emergency Department, these devices are relatively inexpensive; do not preclude physical exam, inguinal vascular access, splinting, or skeletal traction; and can be left in place for a limited period of time until the patient is hemodynamically stable.

The goal of external pelvic compression is stabilization of early clot. Historically, this has been attributed to reduction in pelvic volume; however, some studies suggest that splintage may actually be the mechanism (Ghaemmaghami 2007, Grimm 1989). Cadaveric and biomechanical studies suggest that these devices reduce both pelvic volume and motion in multiple planes (Bottlang JBJS 2002, Bottlang JOT 2002, Prasarn 2013). What is not known, however, is whether these biomechanical characteristics actually improve clinical outcomes. In one retrospective review of patients with pelvic fractures and other risk factors for hemorrhage (unstable pattern, age > 55, or hypotension), institution of an in-hospital pelvic binder protocol did not alter the need for massive transfusion, angioembolization, or exploratory laparotomy; the 24-hour transfusion requirement; or in-hospital mortality relative to those who received no binder or, rarely, CPAS (Ghaemmaghami 2007). In a retrospective review of patients at a different institution with severe pelvic fractures, patients who received a commercial pelvic binder had significantly diminished 24- and 48-hour transfusion requirements and shorter hospital stays than those who received early anterior external fixation (Croce 2007). Additionally, there was a trend toward decreased mortality in patients who received a pelvic binder, though this was not statistically significant.

Data on the safety of circumferential pelvic compression devices, whether from CPAS or commercially available binders, is mainly limited to cadaver studies and case reports. There is a known risk of skin breakdown secondary to strain at the skin-strap interface. The force measured at the interface between the skin and the binder varies between studies and in some studies has been measured above levels thought to cause tissue damage (Knops 2010, Jowett 2007, Bottlang JOT 2002, Hendrick-

## **PATCH – Pelvis Protocol v5**

### **12/20/16**

Thompson 1992). Furthermore, there have been reports of patients sustaining significant injuries secondary to prolonged circumferential binding with pelvic sheets (Schaller 2005). This risk can be extrapolated to the use of commercial pelvic binders but can likely be minimized by removal of the binder as soon as pelvic injury has been ruled out or the patient is hemodynamically stable. The use of backboards in the prehospital environment also increases the risk of skin compromise related to binder use. Cadaveric studies suggest that centering the pelvic binder around the greater trochanters may reduce the potential for skin breakdown since adequate reduction of the pelvis requires the least amount of force at this location (Bottlang JOT 2002).

Over-reduction of the pelvis could potentially injure pelvic viscera or exiting sacral nerve roots in patients with lateral compression type fractures or fractures through the sacral neuroforamina (Tile 1980). In patients with unstable acetabular fractures or hip dislocations, application of a binder could cause additional displacement or damage to the articular surface. Thus, these injuries are generally considered contraindications to pelvic binder use. However, a cadaveric study of binder application to unstable lateral compression fractures failed to demonstrate a significant change in pelvic volume or degree of internal rotation of the hemipelvis compared to the amount of maximal displacement created by the fracture itself (Bottlang JBJS 2002). Other cadaver studies have failed to demonstrate clinically significant over-compression of commercially available devices (Knops 2011). Some manufacturers have designed their binders with a self-regulating compression device that controls the maximal amount of tension applied, theoretically preventing over-reduction, though data on the efficacy of this design is mixed (SAM Pelvic Sling, Knops 2011).

What is not known is whether prehospital use of pelvic compression devices would alter clinical outcomes for patients with pelvic fractures. It seems logical that stabilization of the pelvis even before arrival at a treatment facility may help mitigate the hemodynamic consequences of pelvic fracture and improve both morbidity and mortality. In the prehospital environment, however, these devices would be placed without the use of diagnostic or confirmatory radiography. It is likely that these binders will thus be inappropriately used in some percentage of patients who will later be found to have a relative contraindication to binder use (e.g. lateral compression pelvic fracture) or a different diagnosis altogether (e.g. acetabular, hip, or femur fracture). There is also the risk of skin compromise and the small though not insignificant chance that such an event could preclude operative fixation or otherwise alter patient management.

### **Purpose of the Study**

The goal of our study is to determine whether prehospital use of a commercial pelvic binder will improve morbidity and mortality in patients with pelvic fractures. We hypothesize that prehospital placement of pelvic binders will reduce hemorrhage and need for resuscitation and will improve overall mortality in patients with pelvic fractures. Our primary outcomes will be indicators of hemorrhage (including vital signs, lactate, base excess, volume of blood products required for resuscitation, need for angioembolization or surgical control of bleeding, and length of ICU stay) and 30-day mortality. We will also measure safety events related to binder use. Additionally, we hypothesize that pelvic splinting via external compression will improve patients' pain regardless of whether they have a pelvic, acetabular, or proximal femur fracture. Pain control in the prehospital environment will be addressed as a secondary outcome in this study.

### **Study Design**

Type of Study: prospective, randomized clinical trial

Study Population: adult patients with a traumatic mechanism of injury who are evaluated at the scene by Medic and have injuries concerning for pelvic fracture and/or hemodynamic instability.

*Inclusion Criteria:*

- (1) Age 18 years or older, and

**PATCH – Pelvis Protocol v5**  
**12/20/16**

- (2) Traumatic injury other than ground-level fall (e.g. MVC, MCC, fall from height  $\geq 20$  feet, etc.), *and*
- (3) Complaint of pelvic, groin, or hip pain, *or*
- (4) Pelvic or hip deformity, ecchymosis, or crepitus in an obtunded patient, *or*
- (5) Hemodynamic instability:
  - a. Systolic blood pressure  $\leq 90$  mmHg
  - b. Heart rate  $>100$  BPM

*Exclusion Criteria:*

- (1) Ground level fall.
- (2) Penetrating pelvis injury without frank evidence of fracture.
- (3) Obviously pregnant patients
- (4) Patients who are too small ( $<32$ in) or too big ( $>50$ in) for the binder
- (5) Priority 2 or 3 Trauma

*Representativeness of the Sample:* Our study should capture a large portion of the patients who present to the hospital with pelvic trauma. We chose to exclude patients who sustained a ground level fall. These are low-energy mechanisms of injury less likely to be improved by external pelvic compression, and more likely to have skin compromise.

Definition of Variables:

*Primary Outcome Variables:* These variables will be abstracted from the medical record by research staff.

- (1) Initial heart rate and blood pressure at the scene (pre-hospital)
- (2) Initial heart rate and blood pressure upon arrival at the Emergency Department
- (3) Time of injury, EMS arrival, binder application (if done), ED arrival
- (4) Initial labs upon arrival at the Emergency Department: lactate, base deficit, PT/INR, hemoglobin
- (5) 24-hour transfusion requirements
- (6) 48-hour transfusion requirements
- (7) Need for angioembolization
- (8) Need for surgical control of bleeding
- (9) Length of intensive care unit stay
- (10) Length of hospital stay
- (11) Need for readmission
- (12) 30-day mortality
- (13) Location of pelvic binder upon presentation to the hospital
- (14) Time the binder removed
- (15) Skin compromise attributable to binder use (location and time since binder placement)
- (16) Other complications of binder use (description and time since binder placement)

*Secondary Outcome Variables:* These variables will be reported by non-obtunded patients using a Visual Analog Score in the pre-hospital environment.

- (1) Pain score at presentation
- (2) Pain score at the conclusion of ambulance transfer (upon arrival to the Emergency Department)

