**PATCH – Pelvis Protocol v5**  
**12/20/16**

not the pelvic binder is removed in the ED is based on clinical data (clinical evidence of hemodynamic stability, imaging failing to demonstrate a pelvic fracture) and is at the discretion of the treating physician (generally an emergency medicine physician or trauma surgeon) in the ED. Patients with evidence of hemodynamic instability or concern for ongoing hemorrhage will undergo angioembolization or surgical intervention according to our institution's protocol. Twenty-four and 48-hour transfusion requirements (including packed red blood cells, fresh frozen plasma, platelets, and cryoprecipitate); need for endovascular or surgical intervention for control of hemorrhage; and length of intensive care unit and hospital stay will be determined from the medical record. Thirty days after the injury, the need for readmission and all-cause mortality within this period will be recorded. Demographic and medical variables (BMI, history of cardiac disease, anticoagulant use, initial PT/INR) will also be abstracted from the medical record.

Complications of binder use, including skin compromise, will also be identified, as will the length of time between binder placement and each event. Should such an event occur a formal incident report will be filed with the appropriate hospital agency as well.

The fracture classification will be assigned by a fellowship-trained orthopaedic traumatologist. The type and timing of operative fixation of the patient's pelvic injury, if necessary, will be at the discretion of the treating orthopaedic surgeon.

*Data analysis:* Data analysis will be carried out when all patients have been assigned to either the experimental or control group. In order to determine whether the randomization process produced comparable groups, we will use t-tests and cross-tabulations to compare patients randomized to the pelvic binder group with those randomized to the control group. The following variables will be considered: age, gender, BMI, history of cardiac disease, anticoagulant use, PT/INR at presentation, injury severity score, and Young and Burgess pelvic fracture class. An intention to treat analysis will also be performed.

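### Sixteen unranked primary variables mix outcomes with scene vitals, process data and binder-defined harms, and no outcome test, alpha or multiplicity rule says which result decides the trial

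*Combined protocol and SAP*

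**What the plan says.** The combined protocol and SAP states its primary outcomes twice.

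- **Purpose of the Study** describes an open list: "Our primary outcomes will be indicators of hemorrhage (including vital signs, lactate, base excess, volume of blood products required for resuscitation", followed by angioembolization or surgical control of bleeding, ICU stay, and 30-day mortality. Safety comes in its own sentence: "We will also measure safety events related to binder use".
- **Study Design, Primary Outcome Variables** gives 16 numbered items with no ranking, introduced by "These variables will be abstracted from the medical record by research staff". They include "1) Initial heart rate and blood pressure at the scene (pre-hospital", "4) Initial labs upon arrival at the Emergency Department: lactate, base deficit, PT/INR, hemoglobin", "13) Location of pelvic binder upon presentation to the hospital" and "15) Skin compromise attributable to binder use (location and time since binder placement". A separate secondary list holds two pain scores.

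**Data analysis** (under Methodology) names tests for one purpose: "In order to determine whether the randomization process produced comparable groups, we will use t-tests and cross-tabulations to compare patients randomized" to each arm. PT/INR at presentation is among the variables to be compared. The section then says that an intention-to-treat analysis will also be done, without attaching an endpoint, test or effect measure to it.

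**The concern.** With no ranking and no decision rule, any of roughly 8 to 20 between-arm comparisons could be presented as the primary result. A mixed pattern, such as better lactate with unchanged mortality, has no agreed reading. Choosing the primary outcome after seeing the data would not repair this.

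Two smaller problems come from the same list. A PT/INR difference between arms could be chance imbalance or a binder effect, and the plan treats it as both. The binder's excess risk of skin and device-type complications cannot be estimated when the definition of the event requires a binder.

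**Working it through.** **1. Sort the 16 items.**

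| Items | Nature | Basis |
|---|---|---|
| 1 | Very probably pre-binder | Scene heart rate and systolic pressure feed inclusion criterion 5, and under Randomization the box is opened only after eligibility is applied |
| 3, 13, 14 | Process or exposure | Timestamps, binder position, binder removal time |
| 15, 16 | Binder-defined harms | Require attribution to, or use of, a binder; timed from its placement |
| 2, 4 to 12 | Outcomes that both arms can have | ED vitals, labs, transfusion, interventions, stays, readmission, mortality |

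Check: 1 + 3 + 2 + 10 = 16. The timing of item 1 is an inference. No sentence times the scene vitals against the binder.

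**2. Compare the two lists.** The firm mismatches are these: safety is separate in Purpose of the Study but primary in Study Design, and hospital stay, readmission and items 3, 13 and 14 are absent from the former. PT/INR, hemoglobin and a second transfusion window are not named there but could pass as hemorrhage indicators, so they are not counted.

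**3. Count the possible comparisons.**
- Purpose of the Study: heart rate, blood pressure (reading vital signs as these two), lactate, base excess, blood product volume, angioembolization or surgical control, ICU stay, 30-day mortality = 8. Taking vital signs as one entry gives 7, or 8 if angioembolization and surgery are split.
- Study Design, the ten comparable items: item 2 gives 2, item 4 gives 4, items 5 to 12 give 8; total 14.
- With the four blood products (Collection of data in the hospital environment) tested separately at 24 and 48 hours: 14 − 2 + 8 = 20.

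**4. Chance of at least one false positive.** There is no plan figure to reproduce. Assumptions, none stated in the documents: 5% two-sided per test, no true effect, jointly normal statistics, success claimed on any one test.
- Independent: 1 − 0.95^m. For m = 8, 14, 20: 0.337, 0.512, 0.642. For two-sided tests on jointly normal statistics this is an upper bound (Šidák's inequality).
- Common correlation ρ: 1 − ∫ φ(t) [Φ((1.96 − √ρ·t)/√(1−ρ)) − Φ((−1.96 − √ρ·t)/√(1−ρ))]^m dt, integrated numerically.

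| Tests | Independent | ρ = 0.5 | ρ = 0.8 | ρ = 0.9 |
|---|---|---|---|---|
| 8 | 34% | 25% | 16% | 12% |
| 14 | 51% | 35% | 20% | 14% |
| 20 | 64% | 42% | 22% | 16% |

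Relative to one test at 5%, the extremes are 11.9/5 = 2.4 and 64.2/5 = 12.8.

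**5. PT/INR.** Item 4 makes it a primary outcome and Data analysis makes it a check on randomization. It is drawn on ED arrival, after a field binder could have acted. It cannot serve cleanly as both.

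**6. Harms.** Under Randomization, controls are managed without a study binder. An event that must be attributed to a binder and timed from its placement has no counterpart in such a patient.

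**The case against.** The best defence is that the Study Design list is a data-collection list. It sits under Definition of Variables and groups items by source: record-abstracted items are called primary and patient-reported items secondary. Scene and ED vitals then form a before-and-after pair, as the two pain scores do. This softens the complaint about item 1 and the process items. It does not answer the main point, because Purpose of the Study also states several primary outcomes without ranking, test or alpha.

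The size of the error rate is also open to challenge. Some pairs are strongly related: 48-hour transfusion includes 24-hour transfusion, and hospital stay includes ICU stay. The plan never says that any single significant result would count as success. Both points stand, so the table runs to ρ = 0.9 and is illustrative only.

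A reader might also infer more than the text supports:
- *That item 1 is certainly pre-treatment.* A patient eligible on pain alone need not have had vitals taken before the box was opened.
- *That controls are left out of safety collection.* Primary outcome data are abstracted from the record for enrolled patients. The gap is in the definition. Mortality, readmission and transfusion need no attribution and can still show net harm.
- *That backboards are a rival cause of skin breakdown.* Background and Significance says they raise the skin risk related to binder use, so that sentence gives no support for a competing cause in controls.
- *That fracture class is safe from binder effects.* Binder location is read from pelvic radiographs on arrival, so some images are taken with the binder on.

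**Conclusion.** The concern holds. The protocol has two differing statements of its primary outcomes. The longer one places one very probably pre-binder measure, three process or exposure items and two binder-defined harms among ten usable outcomes. The text from Background and Significance to the references contains no outcome test, alpha or multiplicity rule; front pages were not available, so the absence is asserted only for that text. An intention-to-treat analysis is stated, so it would be wrong to say that there is no analysis plan at all.

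Under the stated assumptions, unadjusted testing would carry a false-positive chance of about 12% to 64%, roughly 2.4 to 13 times 5%. A reader might take 51% or 64% as the trial's error rate; the documents do not support that, since they give no alpha, number of tests, correlation or success rule. The conclusion that no result is designated as decisive does not depend on these figures. The PT/INR and harm-definition faults are real but secondary.

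**What to change.** **(a) Primary outcome.** Reconcile Purpose of the Study with Study Design. Name one primary outcome, chosen by the sponsor, with its time window, test and two-sided alpha in the intention-to-treat population, or two in a fixed sequence or under Holm. Label the rest secondary. State whether the four blood products are pooled. If death is ranked worst in a transfusion outcome, state the window for death.

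**(b) Reclassification.** Move item 1 to baseline covariates and items 3, 13 and 14 to process or exposure data. Remove PT/INR from the comparability check. Report fracture class with the caveat that images may be taken with the binder on.

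**(c) Harms.** In both arms and regardless of attribution, abstract pelvic-region skin breakdown, nerve or visceral injury, and displacement or articular damage in acetabular fracture or hip dislocation, all of which Background and Significance names. Use one window that does not start at binder placement, such as ED arrival to 30 days. Record any pelvic compression received in either arm. Report the between-arm risk difference with 95% CI by intention to treat, and keep attribution and time since placement as descriptive.

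**Cost.** Protocol wording and a few abstraction fields. Other outcomes lose confirmatory status. Skin charting in controls may be less complete, which should be stated as a limitation. Power for mortality may be low, and no sample size is given. For scale only, a two-proportion z-test at 80% power and 5% two-sided, with a one-third relative reduction, needs about 2,260, 1,080 or 490 patients per arm if control mortality is 5%, 10% or 20%. These rates, the reduction, the power and the alpha are all assumptions.

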*Randomization:* Prior to each shift, each ambulance will be randomly assigned an opaque box containing either a commercial pelvic binder or a weight-equivalent object and patient ID tag. When an ambulance arrives at the scene, EMS personnel will apply inclusion and exclusion criteria to determine if the patient is appropriate for this study. If so, EMS personnel will open the opaque box. If the box contains a pelvic binder, the patient will have a pelvic binder placed. If the opaque box contains the weight-equivalent object, the patient ID tag will be clipped to the patient, and the patient will be managed without a binder under the current standard of care. At the receiving facility, EMS personnel will page the research team and fill out the label on the box with information identifying the run number, unit number, and time of dispatch. The box will be placed in a box in the emergency department for research staff to pick up. The removal of pelvic binder on patient will be determined by the appropriate physician team. Pelvic binder should be removed within 72 hours of admission.

*Collection of prehospital outcome data:* At the time of initial assessment by EMS personnel, awake patients will be asked to rate their pain using a visual analog scale (VAS). At the conclusion of ambulance transport, awake patients will again be asked to rate their pain using a VAS. The patient's initial heart rate and blood pressure will also be recorded in the prehospital environment.

*Collection of data in the hospital environment:* Patients enrolled in the study will be identified using the information collected by EMS personnel on the box, the page to research staff, and/or the presence of a pelvic binder or patient ID tag on the patient. Primary outcome data will be abstracted from the medical record. The patient's initial heart rate and blood pressure will be recorded upon presentation to the Emergency Department (ED). Other laboratory data, including lactate, base deficit, hemoglobin, and PT/INR, will be collected upon presentation to the ED. Pelvic radiographs will be obtained as appropriate per standard of care. Both placement and location of the pelvic binder upon arrival will be determined from pelvic radiographs. Whether or

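### Skin compromise and other local complications are recorded only as binder-attributed events, so the trial cannot estimate the between-arm difference in local harm

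*Combined protocol and SAP*

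**What the plan says.** Under Definition of Variables, the primary outcome list ends with two harm items: "15) Skin compromise attributable to binder use (location and time since binder placement" and "16) Other complications of binder use (description and time since binder placement". Both depend on the binder, and both are timed from its placement.

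The same restriction appears in two other places, so it is not a slip in one line. Purpose of the Study states the safety aim as "We will also measure safety events related to binder use". Methodology, on hospital data collection, says "Complications of binder use, including skin compromise, will also be identified, as will the length of time between binder placement and each event".

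The Randomization paragraph says of a control that "the patient will be managed without a binder under the current standard of care". The Data analysis paragraph describes baseline comparability tests and one sentence on intention to treat. It sets out no safety analysis. No section describes an all-cause skin assessment, a rule for attributing an event to the binder, a person who attributes it, or collection of these local harms in controls.

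**The concern.** An outcome that requires exposure to the device cannot occur in a patient who is never exposed. Under intention to treat, such patients enter the denominator with no possibility of an event. The two percentages then measure different things: attributed harm in one arm and, largely, a structural absence in the other.

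Attribution is a weak substitute for a control group here. The harms that Background and Significance fears from over-reduction or misapplication (visceral or nerve-root injury, further displacement, articular damage) resemble what the trauma itself can cause. Skin risk is also not described as a fixed property of the device: the protocol says that backboards add to it, "The use of backboards in the prehospital environment also increases the risk of skin compromise related to binder use", and that patients with ground-level falls, who are excluded, are "less likely to be improved by external pelvic compression, and more likely to have skin compromise". The binder is visible, and its presence is one of the ways enrolled patients are identified. Whoever makes the judgement will therefore probably know the arm, although the plan does not say who that is.

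The stake is the morbidity part of the trial's question. The background describes existing safety evidence as mostly cadaver work and isolated cases, and notes that skin injury might prevent operative fixation. Randomisation could supply an unbiased excess risk, but the present definitions do not use it for local harm.

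**Working it through.** The plan states no skin-event rate, sample size or safety test, so there is no figure of its own to reproduce. The rates below are assumptions that show how the definition behaves.

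**Inputs (assumed).** All-cause pelvic, trochanteric or sacral skin compromise: 5% in controls, 8% in the binder arm. No control is bound, unless stated otherwise.

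**Quantity of interest.** True excess = 8% − 5% = 3 points.

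**What items (15) and (16) would record.** Split the binder-arm 8% into 5% that would have happened anyway and 3% caused by the binder. Let a be the share of the first group attributed to the binder, and b the share of the second. Then:

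recorded binder-arm rate = 5% × a + 3% × b

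| Attribution | a | b | Recorded in binder arm | Recorded in never-bound controls |
|---|---|---|---|---|
| Nothing attributed | 0 | 0 | 0% | 0% |
| Perfect | 0 | 1 | 3% | 0% |
| Half of all events | 0.5 | 0.5 | 2.5% + 1.5% = 4% | 0% |
| Everything attributed | 1 | 1 | 5% + 3% = 8% | 0% |

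The range is 0% to 8% around a true excess of 3 points, and the direction of error is unknown.

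**The record cannot be inverted.** Suppose 4% is recorded in the binder arm. That fits a 3-point excess with half of 8% attributed. It also fits an excess of 4 points with perfect attribution. It fits no excess at all if both arms have a true rate of 8% and half of the binder-arm events are attributed (0.5 × 8% = 4%). Without the control rate and the attribution shares, the data cannot tell these apart.

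**Controls bound later in hospital.** Let the true rate p be the same in both arms, so the binder has no effect. Let a share c of controls be bound after arrival, and let every event in a bound patient be attributed. Then:

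apparent excess = p − p × c = p(1 − c)

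- p = 2%: 2 points at c = 0; 2 × 0.7 = 1.4 points at c = 30%
- p = 5%: 5 points at c = 0; 5 × 0.7 = 3.5 points at c = 30%
- p = 10%: 10 points at c = 0; 10 × 0.7 = 7 points at c = 30%

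Later binding shrinks the artefact but removes it only if every control is bound. These are full-attribution extremes, not forecasts.

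**With all-cause recording in both arms.** The expected difference is 8% − 5% = 3 points in the first example and p − p = 0 in the second, provided ascertainment is equal.

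**The case against.** The best defence is that the safety aim is descriptive. The protocol says that it will measure binder-related events; it does not promise to compare them. Rate, location and timing in bound patients, together with the incident report the protocol requires, fit device surveillance. This stands: a descriptive rate can be reported as planned.

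A reader might infer several stronger things that the documents do not support.

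- *That the safety question as a whole cannot be answered, or that benefit–risk has no valid comparison.* Transfusion, angioembolization, surgery for bleeding, lengths of stay, readmission and 30-day all-cause mortality do not depend on the binder. Only the comparison of skin and other local complications is lost.
- *That the control arm is zero by definition.* This holds for never-bound controls. Nothing forbids a binder after arrival, and the background says "Temporary pelvic splinting with these devices is now recommended in the initial management of hemodynamically unstable patients". A control bound in hospital could have a qualifying event.
- *That harm would be overstated 2.7-fold (8/3).* That needs every background event to be charged to the binder. Perfect attribution gives 3%, equal to the true excess, and no attribution gives 0%. Nor does the plan say that it will compare these items by arm.
- *That the protocol names backboards as a separate cause of skin injury.* It describes them as aggravating binder-related injury. Skin injury in unbound trauma patients is plausible, but the documents do not state it.
- *That unblinded staff make the attribution.* Research staff abstract the variables; who judges cause is not stated.

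What remains is that a descriptive rate does not give the excess risk, and that a randomised trial can obtain that excess at little cost.

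**Conclusion.** The concern holds in this limited form. The two local-harm items yield a descriptive rate of binder-attributed events in bound patients, but no estimate of the between-arm difference in local harm. This follows from the definitions alone and needs no assumed rate.

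The size of the resulting error cannot be taken from the documents. On the assumed 5% and 8%, a true 3-point excess could be recorded as anything from 0% to 8%, against about 0% in never-bound controls. Neither overstatement nor understatement can be claimed in advance. The outcomes recorded regardless of binder use keep their randomised comparison. The plan should be changed because the correction is cheap and serves the morbidity question; the flaw does not undermine the rest of the trial.

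**What to change.** Change the definitions and the abstraction form as follows.

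1. Redefine item (15) as skin compromise over the pelvis, trochanters or sacrum, whatever the cause, in both arms, with location and time from ED arrival.
2. Redefine item (16) as a fixed list of local complications, whatever the cause, in both arms: new neurological deficit, fracture or joint displacement, and pelvic visceral injury.
3. Use one definition, one chart source and one window in both arms, starting at ED arrival and including findings recorded at arrival, since study binders are applied at the scene. State when the window ends. Length of stay is itself an outcome, so a window closing at discharge could give the arms unequal observation time; a fixed day avoids this.
4. Compare both items by randomised arm, giving the risk difference with a confidence interval.
5. Keep attribution and time since placement as descriptive fields for any patient who received a binder, including a control bound in hospital. Say who attributes events and by what rule.
6. Align the safety sentence in Purpose of the Study and the hospital data-collection text with the new definitions.

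The cost is form wording and abstraction of the same fields from control charts, which are already opened for the other outcomes. The remaining weakness is detection: skin over the pelvis may be charted more fully in bound patients, which would inflate the apparent excess. State this as a limitation. A standard skin check in both arms would reduce it, but would be an added procedure.
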